#### Date: June 7, 2024

### **Appendix D: TCOM**

### Technique

Place the subject in the supine position, with the arms and legs at the same level as the heart. Electrodes must be in contact with the tissue through the contact liquid. If there is air between the tissue and an electrode, TCOM values will be questionable. Erroneous readings may also occur if electrodes are placed directly over a bone or there is severe edema around the wound. For the best results, tests should be conducted at ambient temperature (21-23) and the subject should not have smoked, nor had caffeine for several hours prior.

- 1. Calibrate the TCOM electrode—this takes about 15-20 minutes.
- 2. Clean the selected measuring site with acohol or other skin-preparation solution.
- 3. Dry the site well with a gauze pad.
- 4. Take a standard fixation ring.
- 5. Remove the fixation ring from the protective film.
- 6. Apply the fixation ring to the measuring site as follows:
  - Press the center of the fixation ring onto the measuring site with a finger.
  - Run a finger around the firm circumference.
  - Press firmly to prevent leaks.
- 7. Fill the hole in the fixation ring with 3-5 drops of the contact liquid.
- 8. Affix the electrode into the fixation ring as follows:
  - Align the arrow on the electrode with one of the marks on the fixation ring.
  - Turn the electrode 90° clockwise to fasten it in the fixation ring.
- 9. Repeat steps 1 to 8 if more electrodes are to be applied; note: several electrodes can be calibrated at the same time.

It is sometimes advantageous to simultaneously use several electrodes placed strategically around the wound and calculate mean values from individual readings.

The normal sequence of events for TCOM is measurement in air, the leg elevation test (optional) and the oxygen challenge. Shah et al determined that the optimal times for these events in terms of measurement time are 20, 5 and 10 minutes, respectively.

#### Version 1.0 Appendix E: Debridement

Many chronic wounds contain necrotic tissue that has a black or dark gray appearance. Wound eschar is usually full-thickness, dry devitalized tissue arising from prolonged ischemia and slough is an adherent fibrous material commonly creamy yellow in appearance. Chronic wounds can also have colonized bacteria in the form of biofilm or cells, particularly along the margins of a wound, which have stopped dividing - a process known as senescence. Finally, devitalized tissue and biofilms can harbor high levels of cytokines or cellular remnants that maintain the wound in the inflammatory or proliferative stages of healing, through cellular trafficking processes. Any of these factors can disrupt the normal stages of wound healing.

Debridement is the process by which these elements are removed to permit healing, in effect changing the stalled chronic wound into an acute wound. In this clinical study, we have restricted the type of debridement to sharp debridement.

## Technique

Sharp debridement comprises the following elements:

- 1. The target ulcer and the surrounding skin are prepped with water or Saline.
- 2. Anesthesia, topical or injected, is applied to the ulcer as necessary to reduce subject discomfort.
- 3. Using a sterile technique, all non-viable tissue in the wound bed is excised using a scalpel and scissors.
- 4. Excessive bleeding is controlled by using direct pressure, but cautery may be employed if necessary.

If extensive surgical debridement is necessary during the run-in period (e.g., general anesthesia is required), the patient is not a candidate for this trial. Likewise, if other forms of debridement (e.g., enzymatic) are required during run-in, based on the opinion of the treating clinician, the subject should be screen failed. During the Treatment Phase of the trial, other forms of debridement are NOT permitted. If this should happen, the type of debridement should be noted in the CRF, using other forms of debridement besides sharp debridement more than once during the treatment phase will result in the subject being withdrawn from the trial.

Although there is increasing evidence that more frequent debridement results in faster healing on average, the frequency and level of debridement in this trial is left up to the treating physician's judgment. Excessive debridement can be as deleterious to healing as too little debridement.

For wound bed preparation, follow the TIME principles: Tissue management (primarily debridement in this trial), control of Infection and Inflammation (management of infection, control of edema, management of exudate, etc.), Moisture imbalance (ensuring that the wound is at all times in a moist healing environment, as well as dealing with excessive wound exudate), and advancement of the epithelial Edge of the wound (addressing hypoxia, infection, desiccation, dressing trauma, hyperkeratosis and calluses, and cell senescence at the wound margin). (Dowsett C, Newton H. Wounds UK 2005; 1:58-70)

SOC in this study is offloading of the DFU, appropriate sharp or surgical debridement, and infection management as deemed appropriate by the investigator. Patients will be provided with a cast walker to offload their wounds or total contact casting if walkers cannot be made to fit the participant's index foot. Primary dressings for the SOC group are plain foam (Allevyn gentle, Mepilex) or Mepital / Adaptic Touch) and a final three-layer dressing (4x4 gauze, soft cast roll, ace bandage / Coban).

General

Descriptive statistical methods will be used to summarize the data from this study. These include number of subjects (n), mean and standard deviation (SD) for continuous variable data (medians and IQR [interquartile range] values will be given when the distribution of variable values is non-normal), and frequencies and percentages for categorical variable data. There will be no hypothesis testing performed in regard to trial endpoints. All data collected during the study will be reported and analyzed.

Unless specified otherwise, all statistical testing will be two-sided and performed using a significance (alpha) level of 0.05.

All statistical analyses will be conducted using IBM SPSS statistics (v27).

Sample Size Calculations

No sample size calculations were performed as a convenience sample of 24 subjects will be enrolled at up to 5 sites.

Subject Replacement

Not applicable to this study.

Interim Analysis

No formal interim analysis is planned or conducted.

Trial Stopping Rules

Subjects will be permitted to withdraw at any time and investigators can withdraw a patient based on the occurrence of an AE/SAE interfering with treatment or placing the subject's health in jeopardy.

There were no overall trial stopping rules.

Patient Populations

The populations defined for the analysis include intent-to-treat (ITT), per protocol (PP), and safety populations.

Intent-to-treat population (ITT)

The ITT population will consist of all randomized subjects, regardless of actual treatment received, with analysis conducted according to original treatment assignment group. Subjects who were randomized but later found to be ineligible for the study because they failed to meet all inclusion and exclusion criteria will be excluded.

Per protocol (PP)

The PP population will consist of randomized subjects with analysis conducted according to treatment received. The following subjects will be excluded: (a) subjects randomized but later found to be ineligible for the study because they failed to meet all inclusion and exclusion criteria; (b) subjects who did not complete the study; and (c) subjects with major protocol violations.

Safety Population

The safety population will be all subjects who were randomized and received at least one treatment.

Definitions

Baseline

For all parameters, baseline will be defined as the last available data point before the first treatment, which occurs at TV1.

Visit window data including study endpoints

For each weekly visit a window of ± 2 days will be adopted for data. If a specified time endpoint is outside of the window the last available visit data prior to the specified endpoint will be used.

Healing of Index Ulcer

Healing is defined as complete epithelialization of the ulcer without drainage observed in the index ulcer at two separate visits 2 weeks apart. If a subject fails this healing confirmation visit then they can continue in the trial with their assigned treatment provided that the index wound did not heal at the EOS visit.

Date of healing

The date of healing is defined as the date of the first assessment of index ulcer healing provided the index ulcer is still healed 2 weeks later.

Percentage area reduction from baseline

The percent change in the surface area of the Index Ulcer (PAR) will be calculated using the following formula:

((A1-A2)/A1)*100

Where A1 is the baseline area (at randomization), and A2 is the area at the specified time point.

Statistical Methodology

Missing data

Missing data may be the result of missed visits, subjects lost to follow-up or who have died, and may be endpoint data or covariate data.

The outcome of complete wound healing will be scored as **not** healed for the following events:

• The subject dies

- The subject has an amputation that affects the index ulcer
- The subjects is lost to follow-up
- The subjects is withdrawn from the trial
- The subject withdraws consent.

Missing PAR endpoint data within 5 weeks from TV1 will be not imputed.

Data QC

- 1. Inspect for accuracy of input:
 - 1.1. Plausible values
 - 1.2. Outliers or out-of-range values
- 2. Evaluate degree and distribution of missing data; for missing non-endpoint, out-of-range or non-plausible data, query PERI.
- 3. Identify non-normal continuous variables; data for non-normal continuous variables will include median/IQR metrics.

Statistical Analysis

Analysis will be started once database lock for the trial is initiated and the final version of the SAP is released into EnColl's system.

Research hypotheses

Because this trial is not powered to statistically test endpoints, no primary research hypotheses (hypotheses tested using statistical tests) will be tested.

General

The following analyses will be conducted:

- 1. Flow chart (subjects) with disposition according to CONSORT criteria (see shell Figure 1).
- 2. Overall trial statistics (enrollment dates, site numbers, numbers of subjects, group assignments)
- 3. Screen failure rate and screen failure reasons according to exclusion criteria.
- 4. Deaths, withdrawals, and loss to follow-up (total and by group assignment) with week of discontinuation and reason.

Demographics (subject-related and wound-related)

Patient demographics between groups at baseline: patient age, smoking status, BMI, HbA1c and creatinine levels; diabetes duration; number of concurrent DFUs and prior DFUs; amputations (broken down into major and minor amputation counts); history of DFU recurrence; history of and significant foot deformities.

Wound demographics between groups at baseline: DFU positions and location; ulcer duration and area at randomization; offloading type and offloading history; debridement count.

Baseline variables between groups will be tested using t tests, Mann-Whitney, chi square, and Fisher exact tests (as appropriate) without adjustment for multiplicity testing (see shell Tables 1 and 2).

Selected comorbidities will be presented along with total comorbidity count (extracted from medical history; will be tested between treatment groups) (see shell Table 3)

Endpoints

Endpoint analysis will conducted using the ITT population.

Primary

1. Primary endpoint analysis: PAR of index wounds at 5 weeks (mean and SD) by treatment group presented in a table; a separate figure will be presented for both treatment groups for mean PAR at weeks 1-5.

Secondary

The following endpoints will be calculated for each treatment group:

- 2. Proportions of index wounds healed by 5 weeks.
- 3. Time to heal within 5 weeks: mean time to heal (days) with 95% confidence intervals. A Kaplan-Meier plot for both treatment groups will be presented.
- 4. Number of applications of the intervention product for healed wounds only by treatment group.

Analysis will be done for the ITT population.

Safety Analysis

The following will be conducted:

Summary statistics for each treatment group:

- Count of AEs per treatment group/per patient
- Summary rates per group
- Notes of unexpected occurrences during the study; relevant decisions made) (text in report)
- Counts of SAEs/AEs by treatment group (listing of subjects); see shell Table 4.

- Complete listing of all AEs by subject, system organ class and preferred term(s). SAEs will be **bolded** in the listing (see shell Table 5).
- Counts of AEs by severity and relatedness to intervention product (see shell Table 6).

Shell Figure 1. CONSORT subject flow chart. EP: Epifix; HC: Helicoll.

Shell Table 1. Patient-related variables, except for comorbidities and concomitant drugs. Figures in parentheses will be percentage for categorical variables and standard deviation (SD) of the mean for continuous variables; for non-normal variables, such as initial wound area, medians and interquartile ranges (IQR) will be added.

Variable	Epifix	Helicoll	р
Age (years)	XX.X (XX.XX)	XX.X (XX.XX)	XX
Race			
Caucasian	X (X%)	X (X%)	
African American	X (X%)	X (X%)	XX
Other	X (X%)	X (X%)	
Ethnicity			
Hispanic	X (X%)	X (X%)	XX
Not Hispanic	X (X%)	X (X%)	
Gender			
Male	X (X%)	X (X%)	XX
Female	X (X%)	X (X%)	
BMI	XX.X (XX.XX)	XX.X (XX.XX)	XX
Smoker			
Current	X (X%)	X (X%)	
Former	X (X%)	X (X%)	XX
Never smoked	X (X%)	X (X%)	
HbA1c (%)			
At randomization	XX.X	XX.X	XX
Creatinine (mg/dL)	XX.X (XX.XX)	XX.X (XX.XX)	XX
Diabetes duration (years)	XX.X (XX.XX)	XX.X (XX.XX)	XX
Subject age when first DFU			
appeared (years)	XX.X (XX.XX)	XX.X (XX.XX)	XX
Prior DFU count	XX.X (XX.XX)	XX.X (XX.XX)	XX
Other concurrent DFUs (at			
screening	X (X%)	X (X%)	XX
History DFU recurrence	X (X%)	X (X%)	XX
Amputations, minor			
0	X (X%)	X (X%)	
1	X (X%)	X (X%)	
2	X (X%)	X (X%)	XX
3	X (X%)	X (X%)	
≥4	X (X%)	X (X%)	
Major amputations	X (X%)	X (X%)	XX

Variable	Epifix	Helicoll	р
Foot deformities			
Deformity 1	X (X%)	X (X%)	XX
{Continue for all subjects			
with identified different			
deformities}			

Shell Table 2. Wound-related variables. Figures in parentheses will be percentage for categorical variables and standard deviation (SD) of the mean for continuous variables; for variables that have a non-normal distribution of values, such as initial wound area, medians and interquartile ranges (IQR) will be added.

Variable	Epifix	Helicoll	р
Wound area (cm ²)	XX.X (XX.XX)	XX.X XX (XX)	XX
	XX (XX)	XX (XX)	
Wound age (weeks)	XX.X (XX.XX)	XX.X XX (XX)	XX
	XX (XX)	XX (XX)	
Vertical location			
Plantar	X (X%)	X (X%)	XX
Dorsal	X (X%)	X (X%)	
Position			
Medial	X (X%)	X (X%)	XX
Lateral	X (X%)	X (X%)	
Anatomical location			
Тое	X (X%)	X (X%)	
Forefoot	X (X%)	X (X%)	
Midfoot	X (X%)	X (X%)	XX
Heel	X (X%)	X (X%)	
Ankle	X (X%)	X (X%)	
Offloading type:			
Type 1	X (X%)	X (X%)	XX
{Continue with			
summary statistics			
for all subjects with			
identified different			
types of offloading}			
Number of	XX.X (XX.XX)	XX.X (XX.XX)	XX
debridements			

Comorbidity	Epifix	Helicoll	р
СКD	X (X%)	X (X%)	X (X%)
Hypertension	X (X%)	X (X%)	X (X%)
PAD	X (X%)	X (X%)	X (X%)
CHF	X (X%)	X (X%)	X (X%)
Leg edema	X (X%)	X (X%)	X (X%)
Restricted mobility*	X (X%)	X (X%)	X (X%)
Venous disease	X (X%)	X (X%)	X (X%)
Peripheral neuropathy	X (X%)	X (X%)	X (X%)
Any psychiatric condition	X (X%)	X (X%)	X (X%)
Comorbidity count**	XX.X	XX.X	XX

Shell Table 3. Selected comorbidities noted at first physical examination by treatment group.

*Restricted mobility: any subject who uses a walker, wheelchair, crutches or canes, and/or has an inability to move freely because of a physical or mental disability, handicap or restriction.

**Based on all identified comorbidities from medical history.

Shell Table 4. Count of SAEs (bolded) and AEs by subject, and totals by treatment group (figures in parentheses represent percentage of total AEs).

AE Category	Epifix	Helicoll
Subject ID	XX-XXX	XX-XXX
SAE count	х	x
{Continue for all subjects with SAEs}		
TOTAL (SAEs)	xx (xx)	xx (xx)
Subject ID	XX-XXX	XX-XXX
AE count	х	x
{Continue for all subjects with AEs}		
TOTAL (AEs)	xx (xx)	xx (xx)

Shell Table 5. Categorization of AEs by medDRA terms for each subject. For AEs categorized as SAEs, **listings will be bolded**.

TEAE Category	Epifix	Helicoll
Subject ID	XX-XXX	XX-XXX
System organ class	Text	Text
Preferred term(s)	Text	Text
{Continue for all system organ classes for		
each subject. Start a new page for each		
subject}		

Shell Table 6. Categorization of AEs by severity and relatedness.

Figures in parentheses represent percentages for each treatment group.

AE Category	Epifix	Helicoll
Severity		
Mild	xx (xx)	xx (xx)
Moderate	xx (xx)	xx (xx)
Severe	xx (xx)	xx (xx)
Life-threatening	xx (xx)	xx (xx)
Fatal	xx (xx)	xx (xx)
Relatedness		
Not related	xx (xx)	xx (xx)
Unlikely to be related	xx (xx)	xx (xx)
Possibly related	xx (xx)	xx (xx)
Probably related	xx (xx)	xx (xx)
Definitely related	xx (xx)	xx (xx)

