## 9.2 Statistical Analysis

Descriptive statistical methods will be used to summarize the data from this study with no hypothesis testing performed for the endpoints.

A formal Statistical Analysis Plan (SAP) will be created prior to database lock. The primary endpoint analysis will be at 5 weeks and a series of secondary and exploratory endpoints will be analyzed at 5 weeks (PAR will be analyzed at all timepoints). The SAP will provide a more technical and detailed description of the proposed data analysis methods and procedures. Any deviation from the analyses outlined in the protocol will be described in the most current version of the SAP. All statistical analyses will be conducted using PASW 28.

No power analysis was conducted as the numbers of subjects enrolled in this trial are too small.

The populations defined for analysis will include the intent-to-treat (ITT) and per protocol (PP). Additional analysis populations may be defined to evaluate study results. Any additional analysis populations will be defined in the SAP.

Primary analysis: The percentage wound area reduction from TV1 to TV5 measured manually with digital photography

Secondary analysis: The time to achieve complete wound closure of the target ulcer by the end of 5 weeks

The proportion of subjects that obtain complete closure over the 5-week treatment period

Mean number of repeated applications of the Advanced Skin Substitute used to obtain wound closure

Endpoint analysis: The appearance, structural stability, and fragility of the new skin formed are documented at each visit. Any recurrence of the wound also will be monitored.

Safety analysis: Tabular listings of all TEAEs per treatment group will be created using system organ class. Other analysis will be described in the SAP.

Every effort will be made to obtain required data at each scheduled evaluation from all subjects who have been enrolled and treated. Subjects who are withdrawn or lost to followup will be included in the ITT analysis of primary and secondary endpoints using data imputation methods detailed in the SAP. Sensitivity analysis will also be conducted for the primary endpoint using different imputation algorithms.

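### The SAP does not impute missing PAR, the primary endpoint, and plans no sensitivity analysis, although protocol 9.2 promises both; the departure is not labelled

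*SAP*

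**What the plan says.** Protocol 9.2 (Statistical Analysis) makes three commitments:

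- On inclusion: "Subjects who are withdrawn or lost to followup will be included in the ITT analysis of primary and secondary endpoints using data imputation methods", with the methods left to the SAP.
- On robustness: "Sensitivity analysis will also be conducted for the primary endpoint using different imputation algorithms".
- On departures: "Any deviation from the analyses outlined in the protocol will be described in the most current version of the SAP".

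The SAP's Missing data section scores complete healing as not healed after death, an amputation affecting the ulcer, loss to follow-up or withdrawal. For PAR it says only "Missing PAR endpoint data within 5 weeks from TV1 will be not imputed". Under Visit window data it adds: "If a specified time endpoint is outside of the window the last available visit data prior to the specified endpoint will be used".

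Under Endpoints it states "Endpoint analysis will conducted using the ITT population", and defines that population as follows: "The ITT population will consist of all randomized subjects, regardless of actual treatment received". The next sentence of that definition removes randomized subjects later found ineligible. The primary analysis is the mean and SD of PAR at 5 weeks by group, with a figure of mean PAR at weeks 1 to 5. No sensitivity analysis appears. The version history records an initial release and no changes.

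**The concern.** The protocol leaves the choice of imputation method to the SAP. It does not leave open whether to impute the primary endpoint. A SAP that declines to impute, and omits the sensitivity analyses, has departed from the protocol rather than filled in its detail.

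With no hypothesis test, the two arm means are the primary result, and at about 12 subjects per arm one or two absent values can move them visibly. The absences may not be neutral: protocol 5.3 lists among its grounds for withdrawal a deteriorating, infected ulcer with exposed bone, and an infection that does not respond. A subject lost in this way counts as a failure for the healing proportion but may vanish from the primary mean. Reporting n and the withdrawals by group, as the SAP plans, would reveal the loss but would not supply the results the protocol promises.

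**Working it through.** **1. The texts side by side, for PAR only.**

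| Topic | Protocol 9.2 | SAP |
|---|---|---|
| Withdrawn or lost subjects | Included in ITT by imputation | Missing PAR not imputed |
| Sensitivity analysis, primary endpoint | Promised, several algorithms | None listed |
| Departure from protocol | To be described in the SAP | Different rule stated, but not labelled or justified; sensitivity omission not mentioned |

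**2. Which rule governs an absent week-5 area?** If the no-imputation sentence governs, the subject drops out and the mean is observed-case. If the window rule is read broadly, it covers an absent visit as well as a mistimed one, and the last earlier area is carried forward. Footnote [C] to protocol Table 1 gives a withdrawn subject an early EOS1, so an area may exist; the SAP does not say whether it is used.

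**3. Early healers.** Protocol 4.5.4.3 treats the healing visit as EOS1, and 5.1 counts these subjects as completers. The SAP's list of sources of missing data ("Missing data may be the result of missed visits, subjects lost to follow-up or who have died") does not include exit on healing. PAR 100% at the primary timepoint is therefore the natural reading, but it is not stated, and nothing explicit covers their later points in the weekly figure.

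**4. Size.** The plan has no figure of its own to reproduce: it gives no dropout rate, PAR mean or SD. Taken from the documents: 24 subjects, half per group, so 24/2 = 12 per arm. Assumed: completers' mean M in both arms, w withdrawals in one arm only, and PAR equal to L for each withdrawn subject.

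Leaving them out gives a difference of M - M = 0. Including them gives

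((12 - w)M + wL)/12 - M = w(L - M)/12.

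At M = 70:

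| L (%) | w = 1 | w = 2 |
|---|---|---|
| 100 | 30/12 = +2.5 | 60/12 = +5.0 |
| 50 | -20/12 = -1.7 | -40/12 = -3.3 |
| 20 | -50/12 = -4.2 | -100/12 = -8.3 |
| 0 | -70/12 = -5.8 | -140/12 = -11.7 |
| -25 | -95/12 = -7.9 | -190/12 = -15.8 |

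The last row shows that PAR 0% is not a floor: an ulcer that grows has negative PAR. At L = 0, moving M from 50 to 85 changes the shift from -4.2 to -7.1 (w = 1) and from -8.3 to -14.2 (w = 2). With one withdrawal in each arm and equal L, the shift is 0. With two against one, it equals the w = 1 column.

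The protocol synopsis speaks of 24 subjects completed. If 12 per arm complete, the divisor becomes 12 + w. At M = 70 and L = 0 this gives -70/13 = -5.4 (w = 1) and -140/14 = -10.0 (w = 2).

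**5. Weekly figure (assumed case).** With 3 of 12 healed and the rest at 55%, the week-5 point is (3 × 100 + 9 × 55)/12 = 66.25 if healers are kept and 55 if they are dropped, a gap of 11.25 points.

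**The case against.** The strongest reply is that the window rule already brings withdrawn subjects in. Its heading covers study endpoints, it falls back on an earlier visit, and the SAP also undertakes to analyse all data collected. A reader might infer from the no-imputation sentence that the primary mean must be observed-case; the documents do not settle that, and this part of the reply stands. It does not rescue the plan, because the window rule is not presented as imputation, it sits in tension with the no-imputation sentence, and it is one algorithm where several were promised.

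Second, the SAP states its PAR rule openly, so the departure can be called described. That is arguable for the no-imputation sentence, which is visible but neither identified as a departure nor justified. It does not cover the sensitivity analyses, on which the SAP is silent.

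Third, nothing is tested, and n and withdrawals are reported. This is correct and limits the severity.

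Fourth, a reader might infer that omitting withdrawn subjects always flatters an arm. The withdrawal criteria make that plausible, but subjects may also leave while doing better than the completers, and the shift is then positive.

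Last, early healers might be thought to fall out of the primary mean. The protocol's completion rule points the other way; what is missing is an explicit statement. The weekly figure and the order of rules are clarifications and add little weight.

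**Conclusion.** The contradiction between protocol 9.2 and the SAP holds for PAR and should be fixed. It does not extend to the healing proportion, for which the SAP has a rule. The documents support saying that the treatment of a withdrawn subject without a week-5 area is unclear, not that the subject is certainly excluded.

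On the assumptions shown, with PAR between 0% and 100% and M = 70, the difference in means moves by -5.8 to +2.5 points for one one-sided withdrawal and by -11.7 to +5.0 for two. It moves less if withdrawals are balanced and further down if PAR is negative. These are illustrations, not forecasts. No error rate or power is affected, because no endpoint is tested.

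**What to change.** Before database lock, replace the no-imputation sentence with one PAR rule that states:

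- what applies when week-5 PAR is absent: the window rule, an early EOS1 area, or a named imputation method;
- that subjects who exit on closure contribute PAR 100%, including at later points of the weekly figure.

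Add the promised sensitivity analyses as descriptive rows, with n per arm for each. Suitable examples are last observed area carried forward; withdrawn or lost subjects at PAR 0%, labelled as not a bound; and observed cases with healers kept. The primary method is the sponsor's choice. If it stays with no imputation, the SAP should label this as a deviation from protocol 9.2 and still carry the rows.

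The cost is one SAP paragraph and up to three descriptive rows, with no new data, since ulcer measurements are already scheduled at every visit. The downside is that any imputation is an assumption; the rows make that visible.

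The rule cannot be applied unambiguously until two further sets of passages are reconciled, which is additional work. The primary endpoint runs to TV5, Table 1 places the week-5 EOS1 at 4 weeks from treatment, and the SAP follows subjects to 5 weeks after randomization. Protocol 4.5.4.3 has subjects exit at healing, while the SAP requires confirmation 2 weeks later.

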#### Safety Analysis:

1. The number and type of Treatment Emergent Adverse and Serious Adverse Events.

ENC-HEL-DFU-02
Version 1.0
Date: June 7, 2024

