## Infection at Target Ulcer site after Randomization

If infection of the target ulcer site occurs after randomization i.e., after Randomization visit record the infection as an adverse event and treat it as appropriate with oral antibiotics at the discretion of the Investigator.

Note: application of topical antibiotics and anti-microbial dressings to the target ulcer site are prohibited.

A subject with an infected target ulcer that is being treated by the Investigator will remain in the study unless the situation requires an alternative methodology that violates the protocol. Antibiotic interventions will be recorded on the Concomitant Medications CRF, and the event will be categorized as an Adverse Event, serious if it meets the definition of that category. All subjects who show evidence of an ulcer infection must have it reported on an Adverse Event CRF.

All subjects will be instructed to contact the Investigator if signs or symptoms of infection develop prior to their next scheduled visit.

During an episode of infection, the investigator should not continue TCC, if it is being used, until the infection is resolved, and dressings should be changed at least every 72 hours.

Evaluate the skin surrounding the target ulcer for presence of signs such as erythema, edema, and cellulitis.

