## **10.1 SOC Adverse Events**

Since this a post market study involving commercially available SOC dressings of FDA cleared and approved medical devices; adverse events associated with their use may also require reporting to FDA along with the possible reason for the failure of the treatment which may include product handling and other details.

An AE is defined as any unfavorable or unintended sign, symptom or disease that occurs or is reported by the subject to have occurred, or a worsening of a pre-existing condition related to the procedure or medical treatment (device/drug) used. All AEs related to the study procedure or medical treatment, including intercurrent illnesses, must be recorded in the subject's medical records and on the CRF. CTCAE v5.0 will be used for AE reporting.

AEs will be defined as those events that occur after the first study treatment is applied at TV1, through the final study visit. A description of the AE along with the onset date, end date, severity, action taken, treatment, outcome, likely cause and relationship to the study procedure or products will be recorded in the CRF.

AEs associated with each treatment arm will be tabulated and compared at the end of the study. AEs will be elicited through direct questioning, subject reports, and physical examination.

An abnormal laboratory test result is not by itself considered to be an AE unless the Investigator considers the finding of clinical significance that should be reported in such a manner.

The Investigator is responsible for assessing the relationship of the AE to the procedure or medical treatments used and the seriousness and expectedness of the AE at the time of occurrence. A medically qualified person appointed by the Sponsor will also assess this once the Sponsor has been notified of an AE. For enrolled subjects, all AEs that occur during the trial will be documented on the AE CRF.

AEs reported during the study should be followed to resolution of the AE or within thirty days from the end of the study. A final assessment of the outcome will be made at that time.

Each AE related to the study procedure or medical treatment used will be categorized as "serious" or "not serious," based on the definition of a serious adverse event (SAE). A SAE is defined as an AE resulting in at least one of the outcomes described in Section 10.1.3.

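### Adverse-event type is listed subject by subject but never counted by arm, so the type half of the safety endpoint has no arm-level summary

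*SAP*

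**What the plan says.** Protocol section 3 gives the safety endpoint as "The number and type of Treatment Emergent Adverse and Serious Adverse Events". Section 9.2 plans the output: "Tabular listings of all TEAEs per treatment group will be created using system organ class". Protocol Table 4 in section 9.1 likewise asks for a listing by treatment group and system organ class. Section 10.1 goes further: "AEs associated with each treatment arm will be tabulated and compared at the end of the study".

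Section 8.6.3 makes target-ulcer infection after randomisation an AE in every case. The site must "record the infection as an adverse event and treat it as appropriate with oral antibiotics", and "All subjects who show evidence of an ulcer infection must have it reported on an Adverse Event" form.

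The Safety Analysis section of the SAP plans three shells for AEs:

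- Shell Table 4 is headed "Count of SAEs (bolded) and AEs by subject, and totals by treatment group".
- Shell Table 5 is headed "Categorization of AEs by medDRA terms for each subject". It implements the planned "Complete listing of all AEs by subject, system organ class and preferred term(s".
- Shell Table 6 counts AEs by severity and by relatedness in each group.

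The same section also names AE counts per group and per patient, and summary rates by group. For these rates it states neither the event category nor the denominator.

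**The concern.** Shell Table 5 is the only planned output that carries system organ class or preferred term. It has a column for each treatment, but its cells hold text, it has no totals row, and each subject starts on a new page. A reader of the arm-level tables would learn how many events each arm had, how severe they were and how they were attributed, but not what they were.

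This trial does no hypothesis testing on its endpoints, so its descriptive tables are its results. Two arms with quite different kinds of event could look alike at arm level. Target-ulcer infection is the natural example. It has its own protocol criteria and must be reported whenever it occurs, and affected subjects normally stay in the study, yet no SAP output names it.

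**Working it through.** **1. Which planned outputs count type by arm?**

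| SAP output | By arm | Counts | Event type |
|---|---|---|---|
| Shell Table 4 | yes, arm totals | yes | no |
| Shell Table 5 | treatment columns, filled per subject | no | yes |
| Shell Table 6 | yes | yes | no |
| AE counts per group and per patient | yes | yes | not stated |
| Rates by group | yes | rates | not stated, no shell |
| Discontinuations with reason | yes | yes | only where an event ended participation |

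No row is shown to combine arm, count and type.

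**2. Can the arm-level AE tables match while type differs?** The plan has no figure to reproduce, because the documents give no AE or infection rate. From the documents come the 24 subjects (SAP, Sample Size Calculations) and the half-and-half allocation (protocol synopsis): 24 / 2 = 12 per arm. Everything else in this step is assumed.

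- Each arm has 8 AEs in 8 subjects, 1 of them serious.
- Severity in each arm: 4 mild, 3 moderate, 1 severe.
- Relatedness in each arm: 3 not related, 4 possibly, 1 probably related.
- Target-ulcer infection makes up 6 of the 8 AEs in one arm and 1 of the 8 in the other, with at most one per subject.

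Filling the shells:

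- Shell Table 4 totals: 8 v 8 AEs and 1 v 1 SAE.
- AEs per patient: 8/12 = 0.67 in both arms.
- Shell Table 6: 4/3/1 by severity and 3/4/1 by relatedness in both arms, so every cell matches.
- Subjects with infection: 6/12 = 50.0% v 1/12 = 8.3%, a difference of 5/12 = 41.7 percentage points.

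**3. How does this vary with the assumption?**

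- 4 v 1 infections: 3/12 = 25.0 points.
- 5 v 1 infections: 4/12 = 33.3 points.

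For 5 v 1, the Wilson 95% limits are 19.33% to 68.05% for 5/12 and 1.49% to 35.39% for 1/12. The Newcombe interval for the difference is then:

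- lower: 33.33 − √[(41.67 − 19.33)² + (35.39 − 8.33)²] = 33.33 − 35.09 = −1.8 points
- upper: 33.33 + √[(68.05 − 41.67)² + (8.33 − 1.49)²] = 33.33 + 27.25 = 60.6 points

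Even a difference of that size would be imprecise with 12 per arm. The missing table would therefore describe the arms; it would not settle whether they differ.

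**The case against.** Much of the case on the other side stands.

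- **Number is covered.** A reader might infer that the safety endpoint as a whole is never tabulated by arm. That is not so: Shell Table 4 has AE and SAE totals for each treatment column.
- **The protocol asks for listings.** A reader might also infer that sections 9.1 and 9.2 are breached. Both ask for listings by group and system organ class, and Shell Table 5 has treatment columns, so they are arguably met in form. The clearer mismatch is with section 10.1. That sentence does not say by type, but the endpoint in section 3 does, and a text listing paged by subject neither tabulates nor compares the arms on type.
- **The rates by group might include type.** They are undefined, so they cannot be said to exclude it. No text or shell says that they include it.
- **The SAP says generally that all collected data will be reported,** with frequencies for categorical variables. No shell applies this to event type.
- **Counts can be recovered by hand.** With 24 subjects this is true, and it would be wrong to say that the plan leaves type unanswerable. But the unit (subjects or events), the grouping of terms and the denominator would then be chosen after the data are seen.
- **Some infections surface elsewhere.** Those that end participation could appear among the withdrawal reasons by arm. Those treated while the subject stays in the study would not.
- **The stakes are modest.** The synopsis states that there is no formal safety objective. The example is also built so that the tables match.

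**Conclusion.** The point holds as a minor reporting gap. Number, severity and relatedness are tabulated by arm. Type is listed only by subject, and no specified output counts events or subjects by system organ class or preferred term in each arm. The type half of the endpoint, and the comparison of arms promised in section 10.1, are therefore not served by any planned summary.

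The size cannot be estimated from the documents. The example, with 12 per arm and assumed AE data, shows that differences of 25.0 to 41.7 points in target-ulcer infection are compatible with identical arm-level AE tables. It does not suggest that such a difference is likely. Data capture and the efficacy results are unaffected.

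**What to change.** In the Safety Analysis section of the SAP, keep Shell Table 5 as the supporting listing, since it supplies what protocol sections 9.1 and 9.2 ask for. Add one descriptive table in the safety population:

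- **Columns:** the two randomised groups, each with its denominator.
- **Rows:** system organ class, with preferred terms beneath.
- **Cells:** number (%) of subjects with at least one such event, and number of events.
- **SAEs:** a parallel block in the same layout.
- **Target-ulcer infection:** a row of its own, identified from the AE form reports that protocol section 8.6.3 requires. State in advance which reports or coded terms count.

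Also state what the rates by group are rates of, with their denominator.

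The cost is some SAP wording, one extra shell and a short rule for the infection row. Events are already to be coded to MedDRA terms, so no new data collection is needed, and no hypothesis test.
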